6.10.1 Eliciting and Reporting Adverse Events

The investigator will periodically assess subjects for the occurrence of adverse events. To avoid bias in collecting information about adverse events, the investigator should ask subjects the following question: "How have you felt since you were last checked?" All adverse events (serious and non-serious) reported by the subject must be recorded on the source documents and CRFs provided by the sponsor.

In addition, the sponsor's Medical Monitor or its designated personnel must be notified immediately by telephone, email, or fax of any immediately reportable adverse events (IRAE) according to the procedure outlined below. Special attention should be paid to recording hospitalization and concomitant medications.

6.10.2 Immediately Reportable Adverse Events

The investigator must report any serious adverse event (SAE), by telephone, email, or fax, to Theracos or its representative immediately after the investigator becomes aware of the event. An SAE form should be completed and sent by email or fax or overnight courier to the sponsor within 24 h of knowledge of the event.

Non-serious events that require discontinuation of investigational product (including laboratory abnormalities) should be reported to Theracos within 3 working days. The IRAE form should be completed and sent by email or fax or overnight courier to the sponsor.

Subjects experiencing an SAE should be followed clinically until their health has returned to baseline status or no further improvement in condition can be expected with further care. It is expected that the investigator will provide or arrange appropriate supportive care for the subject.

6.10.3 Pregnancy

Women of childbearing potential (WOCBP) who are sexually active must use an effective method of birth control during the course of the study, in a manner such that risk of failure is minimized.

Before enrolling WOCBP in this clinical trial, investigators must review guidelines about study participation for WOCBP. The topics should generally include:

1. General information
2. Informed consent form
3. Pregnancy prevention information
4. Drug interactions with hormonal contraceptives.
5. Contraceptives in current use.
6. Guidelines for the follow-up of a reported pregnancy.

Prior to study enrollment, WOCBP must be advised of the importance of avoiding pregnancy during trial participation and the potential risk factors for an unintentional pregnancy. The subject must sign an informed consent form stating the above-mentioned risk factors and that the consequences were discussed with her.

During the study, all WOCBP should be instructed to contact the investigator immediately if they suspect they might be pregnant (e.g. missed or late menstrual cycle).

If a subject or investigator suspects that the subject may be pregnant prior to investigational product administration, the investigational product administration must be withheld until the

results of serum pregnancy tests are available. If the pregnancy is confirmed, the subject must not receive the investigational product and must not remain or be enrolled in the study. If pregnancy is suspected while the subject is receiving study treatment, the investigational product must be withheld immediately until the result of the pregnancy is known. If pregnancy is confirmed, the investigational product will be permanently discontinued and the subject will be withdrawn from the trial. [Exceptions to study discontinuation may be considered for life-threatening conditions only after consultations with a Theracos Medical Monitor or designated personnel.]

The investigator must immediately notify the Medical Monitor of any female subject who becomes pregnant within 30 days after investigational product exposure. The investigator must record the event on the Pregnancy Surveillance form and forward it to Theracos clinical or designated personnel.

Protocol required procedures for study discontinuation and follow-up must be performed on the subject unless contraindicated by pregnancy (*e.g.*, x-ray studies). Other appropriate pregnancy follow-up procedures should be considered if indicated. In addition, the investigator must report to Theracos, on the appropriate Pregnancy Surveillance form(s), follow-up information regarding the course of the pregnancy, including perinatal and neonatal outcome. Infants will be followed for a minimum of six months.

6.10.4 Procedure for Breaking the Blind

As indicated in [Section 5.5](#) above, the sponsor, study coordinators, pharmacists, study subjects, and the cardiovascular adjudication committee members will be blinded to the treatment assignment during the study period. The investigator should also remain blinded to the subject treatment during the entire study unless knowledge of the subject's treatment is required for clinical care and safety. The Emergency Code Break module in the IWRS is used for such situations. The investigator must confirm the intention to unblind the subject's treatment to obtain the dose information in IWRS. Upon completion of the unblinding, the system will send an alert to designated study team members that an unblinding event has occurred. Documentation of breaking the blind should be recorded in the subject's medical record with the date and time the blind was broken, and the names of the personnel requesting and authorizing unblinding. The treatment assignment will continue to be withheld from the cardiovascular adjudication committee members until all phase 3 studies are completed.

6.10.5 Follow-up of Adverse Events

6.10.5.1 Follow-up of Non-serious Adverse Events

Non-serious AEs that are identified on the last scheduled contact must be recorded on the AE CRF with the current status noted. All non-serious AEs that are ongoing at the time will be recorded as ongoing on the CRF.

6.10.5.2 Follow-up of Post-Study Serious Adverse Events

SAEs that are identified on the last scheduled contact must be recorded on the AE CRF page and reported to Theracos according to the reporting procedures outlined in [Section 6.10.2](#). These may include unresolved previously reported SAEs, or new SAEs. The investigator should follow these SAEs until the events are resolved, or the subject is lost to follow-up. Resolution means the subject has returned to the baseline state of health, or the investigator does not expect any further improvement or worsening of the subject's condition. The investigator should continue to report any significant follow-up information to Theracos until the event has been resolved.

Any new SAEs reported by the subject to the investigator that occur after the last scheduled contact, and are determined by the investigator to be reasonably associated with the use of the investigational product, should be reported to the Theracos or designated personnel. This may include SAEs that are captured on follow-up telephone contact or at any other time point after the defined study period (*i.e.*, up to last scheduled contact). The investigator should follow SAEs identified after the last scheduled contact until the events are resolved, or the subject is lost to follow-up. The investigator should continue to report any significant follow-up information to the sponsor until the event has been resolved. This study requires that subjects be actively monitored for SAEs at least 14 days after the last treatment.

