3.2.2 Treatment Period

The 12- week treatment period will start at randomization. At the start of the treatment period each subject will be provided with the investigational products, dosing instructions, and a glycemic control diary in which to record SMBG measurements. Information related to the occurrence of hyperglycemic or hypoglycemic events will be recorded. The investigational products will be orally administered in the morning prior to eating or drinking; the medication should be taken with water. Rescue medication for hyperglycemia will be allowed when deemed medically necessary by the investigator.

Each subject will be instructed to return to the clinic at weeks 2, 6, and 12 for safety and efficacy evaluations including review of adverse events and concomitant medications, vital signs, ECG, physical examination, and blood and urine specimen collections. On the day of the clinic visit a minimum fasting period of 10 hours (h) must be confirmed prior to blood draw.

Subjects will return to the clinic for a follow-up exit visit at week 14 or 2 weeks after the last dose of investigational product. Following the exit visit, subjects will be advised to see their primary physician to undergo treatment to control their diabetes. The duration of participation for each subject is up to 29 weeks based on the treatment status of each potential subject.

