3.4 Study Duration and Dates

Diabetic subjects will be screened within 3 weeks of enrollment. Eligible subjects who provide written consent will start a 2 to 12 week washout and run-in period prior to randomization to receive investigational product. Subjects will receive 12 weeks of treatment and be followed for 2 weeks after the last dose. The study duration from screening to follow-up will be 16 weeks and up to 29 weeks overall (Figure 3). For details of the schedule and nature of the investigations, see the Schedule of Events in [Appendix 1](#).

[figure not shown]

Figure 3. THR-1442-C-449 Study Design

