5.9.2 Investigational Product Kit

One investigational product kit contains a bottle of 90 bexagliflozin tablets, 5 mg, 10 mg, 20 mg, or placebo.

The label attached to each investigational product kit will contain the following information: the kit number, protocol number, product identification, blinded batch number, subject number, storage conditions, sponsor's name and address, CRO or ICCR name and address, investigator's name, and the investigational drug caution statement.

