Participation in a clinical trial is voluntary. A subject can withdraw from the study at any time. The sponsor or investigator may terminate the study for medical or administrative reasons. If a decision is made to withdraw a subject from the study, no further investigational product should be administered. Even if the subject discontinues study medication, every attempt should be made to complete all required study evaluations and procedures. Reasons for all withdrawals should be recorded on the CRF. Examples of reasons for withdrawal include:

1. A protocol violation has occurred,
2. A serious or intolerable adverse event has occurred,
3. A clinically significant change in a laboratory parameter has occurred,
4. The sponsor or investigator terminates the study, or
5. The patient requests to be withdrawn from the study.

Subjects who do not complete the study but who have received investigational product should have a follow-up examination, including a physical examination, vital signs, ECG and clinical laboratory tests according to [Section 7](#).

Subjects who withdraw from the study will not be replaced.

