7 STUDY ACTIVITIES

The study activities at each clinic visit listed below are presented in [Appendix 1](#). The required laboratory tests scheduled at each visit are listed in [Appendix 2](#). Detailed study procedures are described in [Section 6](#).

A visit window of ± 3 days is allowed for all visits except visit V1. Visit V1 is to be scheduled 3 days after visit S5 is complete and can be extended to 5 days depending on HbA1c value availability.

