7.4 Exit Visit or Early Termination Visit

7.4.1 Visit V5 (week 14 or two weeks after the last dose of investigational product if a subject early terminates)

At the V5 visit the study investigator will:

- Review SMBG and glycemic control record
- Perform a complete physical examination including weight
- Measure vital signs, including blood pressures, pulse, temperature, and respiratory rate
- Perform a 12-lead ECG measurement
- Draw blood from subjects who have fasted a minimum of 10 h as described in [Section 6.7.2.1](#). The specific laboratory tests scheduled for this visit are listed in [Appendix 2](#)
- Collect clean-catch, mid-stream urine sample for urinalysis in all subjects and for UPT for women of child bearing potential
- Assess adverse events and record concomitant medications: If subjects have an ongoing serious adverse event, the subject should be followed until the adverse event is resolved or returns to baseline. All possible attempts should be made to document resolution of acute and chronic toxicities.

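### The ±3-day window lets the last scheduled visit fall 11 days after the last dose, short of the protocol's own 14-day minimum for SAE monitoring (minor)

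*Protocol*

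**What the plan says.** Protocol 6.10.5.2 states the requirement as a minimum: "This study requires that subjects be actively monitored for SAEs at least 14 days after the last treatment". SAP 2.2.4 likewise runs SAE documentation to 14 days after the last treatment and attaches no causality condition.

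The schedule that has to deliver this is as follows.

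- **Window.** Protocol Section 7: "A visit window of ± 3 days is allowed for all visits except visit V1". Footnote 1 of Appendix 1 and SAP 3.1.9 repeat it.
- **V5.** Protocol 7.4.1 places it at "week 14 or two weeks after the last dose of investigational product if a subject early terminates". Section 3.2.2 says: "Subjects will return to the clinic for a follow-up exit visit at week 14 or 2 weeks after the last dose of investigational product". Section 3.4 says: "Subjects will receive 12 weeks of treatment and be followed for 2 weeks after the last dose". SAP 3.1.9 gives target days of 85 for V4 and 99 for V5.
- **Nothing after V5.** Neither Appendix 1 nor SAP Table 1 lists a later visit or call.
- **After the last scheduled contact.** Protocol 6.10.5.2 treats that contact as the end of the defined study period. New SAEs arising later are covered if the subject reports them and they "are determined by the investigator to be reasonably associated with the use of the investigational product, should be reported". A follow-up telephone contact is mentioned only as one place where such events may come to light.

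**The concern.** The nominal gap between V4 and V5 equals the required minimum, so there is no slack. A symmetric window on a visit that sits exactly on a floor allows the visit to fall below it. A site could then be fully compliant on visit timing and still not have monitored the subject for the stated period.

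At stake are SAEs that begin in the uncovered days. After V5 the protocol's rule is passive (the subject must report) and filtered by causality (the investigator must see a reasonable association). An SAE on day 12 after the last dose, following a day-11 V5 and judged unrelated, lies inside the SAP's documentation period but outside the protocol's post-contact reporting rule.

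**Working it through.** **Inputs.** V4 target Day 85 and V5 target Day 99 (SAP 3.1.9). Window ±3 days for both (Protocol Section 7). Required monitoring at least 14 days (Protocol 6.10.5.2). Remaining tablets are retrieved at V4 (Protocol 7.3.4), so the last dose is assumed to fall on the V4 day or the day before.

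**Nominal gap.** 99 − 85 = 14 days, equal to (14 − 12) weeks × 7. This reproduces the plan's two weeks.

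**In-window ranges.** V4: 85 ± 3 = Days 82 to 88. V5: 99 ± 3 = Days 96 to 102.

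**Gap in days = V5 day − last-dose day.** The first figure is for a last dose on the V4 day, the second for a last dose the day before.

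| V4 day | V5 Day 96 | V5 Day 99 | V5 Day 102 |
|---|---|---|---|
| 82 | 14 / 15 | 17 / 18 | 20 / 21 |
| 85 | 11 / 12 | 14 / 15 | 17 / 18 |
| 88 | 8 / 9 | 11 / 12 | 14 / 15 |

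With V4 and the last dose on target (Day 85), V5 on Day 96, 97 or 98 gives 11, 12 or 13 days. If dosing stops on Day 84, V5 on Day 96 gives 96 − 84 = 12 days. A late V4 has the same effect: with the last dose on Day 88, even an on-target V5 gives 99 − 88 = 11 days.

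**Early terminators.** V5 is tied to the last dose, so the earliest visit is 14 − 3 = 11 days. No assumption about V4 is needed.

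**Is dosing to Day 88 possible?** Protocol 5.9.2: "One investigational product kit contains a bottle of 90 bexagliflozin tablets, 5 mg, 10 mg, 20 mg, or placebo". One tablet daily from Day 1 to Day 88 uses 88 of the 90.

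**Shortfall against 14 days at the earliest in-window V5.**

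- Last dose Day 84: 14 − 12 = 2 days.
- Last dose Day 85, or early termination: 14 − 11 = 3 days.
- Extreme case, last dose Day 88: 14 − 8 = 6 days.

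**Does the choice of anchor matter?** Anchoring V5 to the last dose allows 11 days; anchoring it to week 14 allows 8. Neither guarantees 14.

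**Check of the proposed window (last dose +14 to +17 days).** For last doses on Days 82 to 88, V5 falls between 82 + 14 = Day 96 and 88 + 17 = Day 105. The SAP Week 14 analysis window is Days 93 to 105, so every such visit stays inside it.

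**The case against.** The strongest reply is that the 14-day duty stands on its own. A visit window allows an early booking; it does not cancel a separate obligation, and a site that holds V5 on day 11 still owes monitoring to day 14. SAP 2.2.4 says the same without a causality filter. On this reading only a reminder in the schedule is missing.

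Part of that stands: the duty is binding, and an unscheduled call would satisfy it. But sites work from the visit schedule, which asks for no such call. The section that states the duty also ends the study period at the last scheduled contact and then applies the narrower reporting rule.

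Other points reduce the weight of the concern.

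- The 8-day case needs a late V4, dosing up to that day and an early V5. It is a bound, not a typical value.
- The V5 anchor is less unsettled than it may look. Sections 3.2.2 and 7.4.1 both offer week 14 and two weeks after the last dose, and 3.4 is a summary. The shortfall does not depend on which anchor is used.
- Protocol 1.1.2 reports that most drug-related material is excreted within 48 to 72 hours without accumulation, so the residual drug risk in the uncovered days is probably small.
- SAEs already under way are followed to resolution regardless, and the treatment-emergent definition in SAP 3.9.1 has no cutoff tied to V5.

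**Conclusion.** The concern holds as a minor inconsistency. A completer whose last dose is on Day 85, or an early terminator, can have an in-window V5 at 11 days, 3 short of the minimum. If dosing ends on Day 84 the shortfall is 2 days, and in the extreme case it is 6.

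The completer figures rest on the last dose falling at or just before V4; the early-terminator figure does not. No frequency can be given, because the documents do not describe how visit dates are distributed. The window is the same in all arms, so neither the comparison between arms nor the efficacy analysis is affected.

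**What to change.** State in Protocol Section 7, Section 7.4.1 and footnote 1 of Appendix 1 (with the matching footnote of SAP Table 1) that V5 may not take place earlier than 14 days after the recorded last dose. For completers and early terminators, the V5 window becomes last dose +14 to +17 days in place of ±3 days.

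Subjects who stop drug but remain in the study need a separate line, since Protocol 6.12 wants them kept on schedule: "Even if the subject discontinues study medication, every attempt should be made to complete all required study evaluations and procedures". They can keep V5 at week 14 ±3 days. The earliest such visit, Day 96, is already at least 14 days after any last dose up to Day 82 (96 − 14 = 82).

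The alternative is to leave the ±3 days alone and require a documented AE/SAE telephone contact on or after day 14 whenever V5 is held earlier.

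The cost is a short edit in four places, which needs ethics approval as an amendment (Protocol 10.2), and then either a slightly tighter booking window or an occasional call. The SAP analysis windows do not change.

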6.10.6 Urinary Tract Infections (UTIs)

Events potentially representing UTIs, including cystitis, urethritis, pyelonephritis, or urosepsis, should be carefully evaluated and documentation of signs, symptoms, culture results for infectious agent, and treatment should be undertaken when appropriate.

The investigator should query the subject at every clinical visit for symptoms that may be related to a UTI and, if appropriate, document these events as symptomatic UTI in the CRF unless an alternative diagnosis is present. In addition, a clean catch urine sample will be obtained at all clinical visits and a urinalysis will be performed on that sample at every clinical visit. A positive urinalysis will be defined as one with detectable leukocyte esterase and/or nitrites. If the subject reports symptoms consistent with a UTI or the urinalysis at the clinical site is positive, a urine culture will be performed at the central laboratory. A positive urine culture will be defined as one with $\geq 10^5$ CFU of any species. The investigator may also perform a urine culture using local resources if necessary for clinical care.

6.10.7 Genital Mycotic Infections (GMIs)

The investigator will query the subjects for signs or symptoms that may represent a GMI at all clinical visits. GMIs will be diagnosed based on symptoms and, if appropriate, physical exam and laboratory findings. Investigators must exclude the possibility of sexually transmitted infections before diagnosing GMI. Diagnosis of GMIs must be documented in the CRF.

6.10.8 Hepatotoxicity

If plasma AST and/or ALT concentrations $> 3 \times$ ULN are detected, the investigator will record in the source documents the date corresponding to the date of the laboratory abnormality; the type, frequency, and dose of any concurrent medications or supplements taken by the subject within the 14 days of the detected abnormality; and any symptoms or change in physical exam that have occurred since the prior assessment. The investigator should perform additional laboratory and imaging tests to attempt to establish the cause of the AST and ALT elevations, including ruling out any potential contribution from bone or muscle etiologies.

Any clinically significant increase in hepatic enzymes and specifically any ALT or AST $> 3 \times$ ULN requires immediate repeat test within 48 to 72 h to confirm the hepatic enzyme elevation and should be repeated based on the clinical situation at least every 96 h (4 days) until ALT and AST return to $< 2.5 \times$ ULN. Study medication should be stopped and the event should be reported as a laboratory adverse event within the CRF if the enzyme elevation is confirmed or worsening.

Hepatotoxicity will be diagnosed and entered as an AE should any of the following occur:

- ALT or AST $> 8 \times$ ULN;
- ALT or AST $> 3 \times$ ULN and total bilirubin $> 2 \times$ ULN or INR > 1.5
- ALT or AST $> 3 \times$ ULN with the appearance of fatigue, nausea, vomiting, right upper quadrant pain or tenderness, fever, rash, and/or eosinophilia ($> 5\%$).

In the event of hepatotoxicity, investigational product should be permanently discontinued. The investigator is encouraged to consult with the Medical Monitor regarding diagnostic evaluation for the hepatic enzyme elevations. Consultation with a hepatologist may also be appropriate in some circumstances.

6.10.9 Hypoglycemia

Events of hypoglycemia or potentially representing hypoglycemia should be carefully evaluated.

All subjects will be provided with a glucometer and diary for recording blood glucose measurements and signs and symptoms of hypoglycemia. During the study the subject is expected to record daily SMBG readings and all signs and symptoms that may potentially reflect hypoglycemia. In the event of such signs or symptoms, the subject is expected to check the blood glucose if it is reasonably safe to do so, and consume carbohydrates, if appropriate, to treat hypoglycemia.

The subject will be expected to record in the glycemic control diary the following information for each hypoglycemic event:

1. Signs and symptoms attributed to hypoglycemia and the time and date on which they occurred
2. SMBG reading at the time of the signs and symptoms attributed to hypoglycemia
3. Time elapsed from the most recent meal to the onset of signs and symptoms
4. Duration, intensity, and type of any exercise within the 24 h prior to the signs and symptoms
5. Type of treatment used (e.g., juice, crackers) for the signs and symptoms and whether assistance was required from another person to administer the treatment
6. SMBG reading 15 minutes after treatment with carbohydrate and the time at which this was measured
7. Whether or not the signs and symptoms attributed to hypoglycemia resolved after blood glucose returned to normal.

Subjects are encouraged to call the study clinic should signs and symptoms potentially related to hypoglycemia occur.

At each study visit, the investigator is expected to review the glucometer and glycemic control diary with particular attention to any SMBG value ≤ 70 mg/dL and any recorded signs or symptoms potentially related hypoglycemia. In addition, the investigator should query the subject with regard to the occurrence of signs and symptoms potentially related to hypoglycemia even if none are recorded in the diary.

In the event of a blood glucose value ≤ 70 mg/dL or signs and symptoms potentially related to hypoglycemia, the investigator should complete the supplemental CRF which will include data from the glycemic control diary and action items to reduce future hypoglycemia episodes.

Hypoglycemia events will be recorded in the hypoglycemia log under 5 categories:

1. Severe hypoglycemia: an event requiring assistance by another person to actively administer carbohydrate, glucagon, or other resuscitative actions. These episodes may be associated with sufficient neuroglycopenia to induce seizure or coma. Plasma glucose measurements may not be available during such an event, but neurological recovery attributable to the restoration of plasma glucose to normal is considered sufficient evidence that the event was induced by a low plasma glucose concentration. All such events should be recorded as serious adverse events in the CRF.
2. Documented symptomatic hypoglycemia: an event during which typical symptoms of hypoglycemia are accompanied by a measured plasma glucose concentration ≤ 70 mg/dL (3.9 mmol/L).
3. Asymptomatic hypoglycemia: an event not accompanied by typical symptoms of hypoglycemia but with a measured blood glucose concentration ≤ 70 mg/dL (3.9 mmol/L).
4. Probable symptomatic hypoglycemia: an event during which symptoms of hypoglycemia are not accompanied by a blood glucose determination but that is presumably caused by a blood glucose concentration ≤ 70 mg/dL (3.9 mmol/L).

5. Relative hypoglycemia: An event during which the person with diabetes reports any of the typical symptoms of hypoglycemia, and interprets those as indicative of hypoglycemia, but with a measured plasma glucose concentration > 70 mg/dL (3.9 mmol/L).

While each event meeting the criteria above will be entered into the hypoglycemia log, only critical hypoglycemia, documented symptomatic hypoglycemia, asymptomatic hypoglycemia, and probable hypoglycemia will be entered as AEs.

In the event of asymptomatic hypoglycemia, the investigator should review the signs and symptoms of hypoglycemia with the subject to elicit a complete description and should review proper glucometer technique to ensure that the low glucose value is not due to improper use of the glucometer.

The investigator should be alert to the likelihood of improper glucose measurement technique if a study subject reports an SMBG value < 55 mg/dL that is not associated with any signs or symptoms of hypoglycemia and is not treated by some form of glucose administration.

In the event of probable symptomatic hypoglycemia, the investigator should encourage the subject to obtain glucose values, when possible, in the context of signs and symptoms of hypoglycemia, even if the glucose value is measured after treatment for the symptoms is administered.

If hypoglycemia occurs in any subject prescribed rescue medication for hyperglycemia during the study, the total daily dose of the rescue medication should be reduced 50% or more at the discretion of the investigator.

